48 versus sensor-augmented pump (SAP) therapy for hypoglycemia prevention in subjects with
49 type 1 diabetes and hypoglycemia unawareness and/or risk for hypoglycemia.

[figure not shown]
50 Subjects: We will recruit up to 85 subjects aged 12-70 years old with type 1 diabetes
51 for at least the past 1 year, on insulin for at least the past 1 year, and on insulin pump
52 therapy for at least the past 6 months to achieve a goal of 44 completed subjects.

53 Subjects will be recruited at two clinical sites: University of Virginia and Stanford
54 University.

55 Procedure: Figure 1 below presents the overall flow of the study.

56

Figure 1: Study flow diagram

Visit 1: Screening 1 Visit. A meter ± CGM download will be performed to evaluate subject

60 eligibility (i.e. Average Daily Risk Range [ADRR] >40 or LBGI >2.5 from SMBG data or
61 LBGI >1.1 from 1 week of CGM data within the prior 3 weeks) and to determine pre-study
62 CGM use in the prior 4 weeks (active [CGM use \geq 5 days/week] or no CGM use). Baseline
63 HbA1c, hypoglycemia symptom awareness (presence of adrenergic symptoms at BG 60
64 mg/dL) and hypoglycemia questionnaires (Clarke Hypoglycemia Perception Awareness and
65 Fear of Hypoglycemia – APPENDIX A-5) will be assessed. Those subjects that qualify will
66 be trained to use the study glucometer and CGM in blinded mode and complete 1 week of
67 baseline blinded CGM and SMBG at least 4 times daily.

68

69 **Visit 2: Screening 2 Visit.** The blinded CGM will be downloaded and if review of the data
70 shows that the CGM was functional >80% of the time and the subject has confirmed risk of
71 hypoglycemia with LBGI >1.1 (#2) (per 1 week of blinded CGM), the subject will be
72 randomized to USS Virginia AP system experimental treatment or Sensor-Augmented Pump
73 Therapy control treatment and proceed to Visit 3. The experimental and control groups will
74 be matched for LBGI and pre-study CGM use. The study glucometer will be downloaded
75 and assessed for average SMBG/day and randomness of data. Subjects with average SMBG
76 <3.5/day and/or poor randomness of SMBG testing will be reminded of SMBG requirements
77 4-6 times daily (pre-meal, bedtime, before driving, before exercise, and as indicated). CGM
78 data collection period may be repeated.

79

80 **Visit 3: 8 hr Inpatient Assessment of Hypoglycemia Counterregulation and Symptom**
81 **Awareness.** The subjects will undergo hypoglycemia induction via a previously validated

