- 392 ○ Oral glucocorticoids
- 393 ○ Pseudoephedrine
- 394 ○ Any other medication that the investigator believes is a contraindications to the
- 395 subject's participation

396

397 **Restrictions on use of other drugs or treatments:**

- 398 ● Acetaminophen will be restricted starting 24 hours prior to CGM use and continuing
- 399 through the entire study.
- 400 ● Caffeinated products will be restricted on the day of Visit 3 and Visit 6 until sampling of
- 401 blood for epinephrine is completed.
- 402 ● Study procedures will be put on hold if acetaminophen use is medically necessary. A
- 403 need for repeated doses may result in stopping study participation at the discretion of the
- 404 investigator.
- 405 ● The CGM sensor will be removed if MRI is needed. Study procedures will be put on
- 406 hold and continued subject participation will be at the discretion of the investigator.
- 407 ● The subject should not donate blood for other purposes while enrolled in this study.
- 408 ● A medical need for oral or injected glucocorticoids will result in stopping study
- 409 participation.
- 410

411 **G. STUDY TIMELINE**

412 **1. Visit 1: Screening 1 Visit**

413

414 At the Screening Visit, the following procedures will be performed / criteria will be

415 checked and documented:

- 416 ● Signed and dated informed consent +/- assent if applicable

- 417 • Inclusion and exclusion criteria
- 418 • Meter and CGM (if CGM user) download from prior 30 days to assess LBG1
- 419 and ADRR
- 420 • CGM download from prior 4 weeks (if CGM user) to assign subject to one of
- 421 two pre-study CGM groups:
- 422 ○ Active user: CGM use ≥ 5 days/week
- 423 ○ Non-user: No CGM use
- 424 • Clarke Hypoglycemia Perception Awareness survey
- 425 • Fear of Hypoglycemia questionnaire
- 426 • Demographics (date of birth, gender, race and ethnicity)
- 427 • Medical history
- 428 • Details of the diabetic history: duration of disease (number of years), diagnosis
- 429 details, current treatment (including basal rates, carbohydrate ratios, insulin
- 430 sensitivity factors, target glucose, average total daily insulin over 7 days,
- 431 hypoglycemia awareness and adrenergic symptom assessment, history of DKA,
- 432 history of severe hypoglycemia, and SMBG values)
- 433 • Past and current medical conditions
- 434 • Surgical history
- 435 • Menstrual history (females), sexual activity and contraceptive use agreement
- 436 • Allergies
- 437 • Medications and supplements

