 517 bedtime), and as needed to calibrate the CGM. Additional
 518 fingersticks may be obtained, if desired.
- 519 • If a subject is a CGM-wearer at screening, the subject may continue to
 520 use the home CGM during blinded study CGM use.

521
 522 The screening visit and training session will last approximately 3 hours. This
 523 may be shorter depending on the amount of pre-screening that was performed
 524 and the subject’s prior knowledge of study devices.

525
 526 If the subject cannot schedule Visit 3 within 4 weeks of screening, the
 527 inclusion and exclusion criteria will be re-evaluated. The study physician will
 528 have the discretion to repeat any test as needed.

529
 530 **2. Visit 2: Screening 2 Visit**

531 After completion of 1 week of baseline blinded CGM use, the subject will return to have the
 532 Dexcom CGM and study glucometer downloaded to assess the subject’s baseline risk for
 533 hypoglycemia and evaluate the reliability of CGM data collection. The meter data will be

534 assessed for average SMBG/day and randomness of data. Subjects with average SMBG
535 <3.5/day and/or poor randomness of SMBG testing will be reminded of SMBG requirements
536 4-6 times daily (pre-meal, bedtime, before driving, before exercise, and as indicated).
537

538 In order to continue with the trial, the subject must have all of the following:

- 539 • Baseline LBGI >1.1 as assessed by the prior 1 week of blinded CGM data
- 540 • CGM must have been functional >80% of the time (i.e. >1600 CGM data
541 points/week).

542
543 CGM data collection period may be repeated. Eligible subjects will be scheduled for
544 Visit 3 within 3 weeks of Visit 2. Subjects will be randomized to experimental
545 treatment with the AP system+USS Virginia or control treatment with sensor-
546 augmented pump therapy. Groups will be matched for LBGI and pre-study CGM
547 use.
548

549 **Preparation for Visit 3:**

- 550 • All subjects will be given written instructions to bring their pump supplies,
551 glucometer supplies, CGM supplies, insulin and all of their current
552 medications (including aspirin or regular analgesics) with them for use during
553 the admission.
- 554 • These instructions will also advise the subject to contact the study team in the
555 event of a febrile or vomiting illness within 24 hours of the admission, so that
556 the admission can be rescheduled.
- 557 • The subject will be asked to avoid the need for a pump site change during Visit
558 3.

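### The pre-study CGM factor has no level for intermittent users, the baseline week differs in kind by CGM status, and the analysis section uses neither matching factor

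*Combined protocol and SAP*

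**What the plan says.** **The factor.** Section G.1 (Visit 1) uses a "CGM download from prior 4 weeks (if CGM user) to assign subject to one of" "two pre-study CGM groups". The first is "Active user: CGM use ≥ 5 days/week" and the second is "Non-user: No CGM use". Section B gives the same two levels in the Visit 1 paragraph, ending "5 days/week] or no CGM use".

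**Its use in allocation.** Section B (Visit 2) says the two arms will "be matched for LBGI and pre-study CGM use", and section G.2 repeats this. Neither describes the method.

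**The baseline week.** Under section G.1 the study CGM is switched to blinded mode for one week in non-pilot subjects. A subject who already wears a CGM at screening may nevertheless "use the home CGM during blinded study CGM use". Section G.2 takes the entry requirement of LBGI above 1.1 from this week. Sections D and J take the baseline of the primary endpoint from it, to be set against the last week of intervention.

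**The analysis.** Section L holds the sample-size argument and mentions intention-to-treat and per-protocol analyses. It names no test, model, covariate, stratified analysis or summary by CGM group.

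**The concern.** There are three linked gaps.

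1. A factor used to balance the arms should place every randomized subject in exactly one level. This one leaves out anyone who uses CGM on some days but on fewer than 5 a week.
2. The baseline week is not the same condition for everyone. Non-users have no readings to act on, while wearers may watch their own device. In the control arm, a non-user's change in LBGI reflects starting CGM with the home pump. A wearer who kept the home CGM was already on CGM with a pump, so that change is largely a continuation of the same therapy.
3. The sponsor thought LBGI and CGM use important enough to match on, but the analysis section does not carry them forward. Balancing on a prognostic factor and then ignoring it discards the precision that the balancing was meant to buy.

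At stake are how the change from baseline is interpreted, the precision of the primary comparison, and an allocation step that is undefined for some subjects.

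**Working it through.** **Are intermittent users eligible?** No inclusion or exclusion criterion in section F removes them, and one criterion can admit them: LBGI above 1.1 from one week of CGM readings in the prior three weeks. A subject whose only CGM use in the four-week window was that week averages 7/4 = 1.75 days a week. That is neither 5 or more nor none. The documents do not say how many such subjects to expect. If 5% to 30% of the 44 completers were intermittent users (assumed), that is 44 × 0.05 = 2.2 to 44 × 0.30 = 13.2, or about 2 to 13 subjects. The number could also be zero.

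**Is the wearers' baseline unblinded?** Section G.1 blinds only the study device, and nothing blinds the home device. That wearers can see their readings is an inference, but a direct one. The permission applies to any wearer at screening, a term the protocol does not define and which is broader than the active-user level. Intermittent users can therefore fall under it too.

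**What does ignoring the factor cost?** The plan has no figure of its own to reproduce. It gives no SD for LBGI, no share of CGM users and no allocation ratio.

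Let *p* be the share of CGM users and *d* the difference in mean LBGI change between CGM groups, in units of the SD within a group. The factor adds *p*(1 − *p*)*d*² to a within-group variance of 1. With arms balanced on the factor, the unadjusted standard error is too large by

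ratio = √(1 + *p*(1 − *p*)*d*²).

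With an equal split (*p* = 0.5):

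| *d* (assumed) | added variance | share of total variance | ratio |
|---|---|---|---|
| 0.25 | 0.0156 | 1.5% | 1.008 |
| 0.5 | 0.0625 | 5.9% | 1.031 |
| 1.0 | 0.25 | 20% | 1.118 |

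With *p* at 0.3 or 0.7 the ratios are 1.007, 1.026 and 1.100.

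**In terms of power.** Assume 22 per arm (half of 44) and a true effect of 0.845 SD, chosen so that power is 0.80 without the extra variance: (1.960 + 0.842) × √(2/22) = 0.845. At *p* = 0.5, power falls to 0.794, 0.776 and 0.708. Those values count the extra variance as sampling error as well. Under exact matching only the reported standard error is inflated, and power is Φ(0.845/√(2/22) − 1.96 × ratio) = 0.80, 0.78 and 0.73.

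**Can the trial test whether the effect differs by CGM group?** The interaction detectable with 80% power is 2.802 × √(4/*n*₁ + 4/*n*₂), where *n*₁ and *n*₂ are the CGM group sizes.
- Equal groups of 22: 2.802 × √(8/22) = 1.69 SD.
- A 30/70 split (13.2 and 30.8): 1.84 SD.

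The main effect needs 2.802 × √(4/44) = 0.84 SD, so a formal interaction test is out of reach.

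**The case against.** Four points can be made for the plan.

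*No bias is shown.* The primary aim compares arms. Two kinds of baseline, balanced across arms, need not distort that comparison; every subject passes the same LBGI threshold; and LBGI remains a matching factor even for a subject with no CGM level. This stands. An oversized standard error is also conservative.

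*Home CGM in the baseline week is an open design choice.* For a wearer it gives a usual-care baseline, and the blinding refers to the study sensor. This stands too. The point is that the difference should be recorded and reported.

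*The size is assumed.* No document gives the difference in change between CGM groups. At 0.25 SD the loss is under 1%. This stands, so the figures show a range and are not an estimate.

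*Section L names no primary model at all.* Its silence on the matching factors is part of that wider gap and need not be a decision to leave them out. This is fair. Still, an analysis that follows the section as written would use neither factor.

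A reader might go further and infer that sites pick the level for unclassified subjects, with knowledge of the arms, so that allocation is open to manipulation. The documents do not support that. They do not say who classifies subjects or by what procedure; they show only that the rule is missing.

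**Conclusion.** The point holds as a minor one. The CGM matching factor is not exhaustive, the primary baseline differs in kind between wearers and non-users, and neither matching factor appears in the analysis section.

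The consequence is lost precision and a change from baseline with a mixed meaning. The unadjusted standard error is too large by about 1%, 3% or 12% for assumed differences of 0.25, 0.5 or 1.0 SD and an equal split. The upper figure should not be read as expected, because nothing in the documents places the true difference within that range.

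A reader might also infer that the treatment comparison is biased. It need not be where matching works. For subjects with no defined level, balance on this factor is not assured, but the documents give neither their number nor any sign of imbalance.

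**What to change.** - **Primary model.** Compare last-week LBGI between arms, adjusted for baseline LBGI and pre-study CGM group. These are the two factors the trial already matches on.
- **CGM levels.** Make them exhaustive, either by adding a third level for intermittent use or by using any use versus none. Do not pool intermittent users with non-users: intermittent wearers may watch their own device in the baseline week, so pooling would mix the two kinds of baseline within one level.
- **Baseline week.** Record whether each subject actually used a home CGM.
- **Reporting.** Show the primary result by CGM group descriptively, without a formal interaction test, and state that wearers' baseline was not blinded.

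**Cost.** One degree of freedom for baseline LBGI and one or two for CGM group, so two to three in all, plus one recorded item. A third level may be small if few intermittent users enroll; any use versus none avoids that.

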- 559 • The subjects will be asked to arrive at the unit fasting and to not consume
560 caffeine on the morning of admission.
- 561 • Subjects will be asked to check a fingerstick BG at 03:00 and 06:00 on the
562 morning of admission for Visit 3 and to aim for a steady BG between 100-150
563 mg/dL upon arrival to the research unit at 07:00.
- 564 • The subject may administer a correction bolus of insulin to stabilize BG or treat
565 hyperglycemia.
- 566 • The subject may consume fast acting glucose (glucose tablets, gel or liquid) to
567 stabilize BG or treat BG <100 mg/dL.

568
569 Visit 2 is anticipated to last approximately 30 minutes.
570

571 **3. Visit 3: 8 hr Inpatient Assessment of Hypoglycemia Counterregulation and** 572 **Symptom Awareness** 573

574 Visit 3 will occur within 4 weeks of the Screening Visit (Visit 1).

575

576 **Admission Overview:**

577 The subject will be admitted to the research unit by 07:00 for a blinded assessment of
578 hypoglycemia counterregulation and symptom awareness. After a Run-in Period for
579 stabilization of the subject's BG in the ~100-150 mg/dL range, the subject will
580 participate in a previously validated Hypoglycemia Induction (#1) where the home
581 insulin pump therapy will be used to induce an episode of hypoglycemia with goal
582 glucose of <60 mg/dL. After carbohydrate rescue to BG \geq 80 mg/dL, the subject will
583 receive a meal and will be monitored for at least an additional hour in the Recovery
584 Period. The subject may then be discharged once the glucose is stable (i.e. at least
585 the prior 2 values) between 100-300 mg/dL and fingerstick ketone level <0.6
586 mmol/L. The subject will additionally receive training on the Dexcom CGM as
587 needed and will receive supplies and instructions to complete the next portion of the
588 study. The specific details of the ~8 hour inpatient admission are provided below.

589

590 **Clinical Research Unit (CRU) Procedures:**

- 591 • A nurse will be at the bedside or on the unit throughout the study.
- 592 • Study staff (MD or NP who has experience in diabetes management) will
593 also be immediately available at the bedside or on the unit throughout the
594 entire study.

595

596 **Blood Sampling and Hypoglycemia Symptom Questionnaires**

- 597 • The clinical centers will either use reinfusion of blood or will discard blood
598 with each blood draw depending on the standard practice at each center's
599 Clinical Research Unit.

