- 600 • Subjects and parents (or diabetes care partners) will be blinded to the results
601 of the glucose testing until the Recovery Period in an attempt to eliminate
602 bias when answering questions regarding symptoms of hypoglycemia.
- 603 • Once IV access has been established, blood will be sampled for YSI glucose
604 every 5-30 minutes. The frequency of blood draws for YSI sampling is
605 dependent on the value of the previous sample, according to the following
606 ranges:
 - 607 ○ BG >200: every 30 minutes
 - 608 ○ BG >100-200: every 15 minutes
 - 609 ○ BG \leq 100 mg/dL: every 5 minutes
- 610 • Blood may be sampled for YSI glucose as needed for patient safety or to
611 recheck a suspected erroneous value (e.g. dilute sample).
- 612 • Blood will be sampled for epinephrine and glucagon and Hypoglycemia
613 Symptom Questionnaires will be performed during the admission as follows:

- 614
- 615
- 616
- 617
- 618
- 619
- 620
- 621
- 622
- 623
- 624
- 625
- 626
- 627
- 628
- 629
- 630
- 631
- 632
- 633
- 634
- 635
- 636
- 637
- 638
- 639
- 640
- 641
- 642
- 643
- 644
- 645
- 646
- 647
- 648
- 649
- 650
- 651
- 652
- 653
- **Run-in Period:**
 - Blood will be sampled for epinephrine at the initial sampling time for YSI glucose after the IV access is established.
 - Once BG is between 100 to 150 mg/dL, baseline Hypoglycemia Symptom Questionnaires will be completed and blood will be sampled for epinephrine and glucagon at the next scheduled sampling time for YSI glucose.
 - **Hypoglycemia Induction Period:**
 - Blood will be sampled for epinephrine approximately every 15 minutes once the blood glucose has decreased to ≤ 90 mg/dL with goal of epinephrine sampling at BGs of 90, 75, 60 and < 60 mg/dL.
 - Blood will be sampled for glucagon when the blood glucose is < 60 mg/dL, just prior to the administration of hypoglycemia rescue therapy.
 - A Hypoglycemia Symptom Questionnaire will be completed approximately every 15 minutes once the blood glucose has decreased to ≤ 90 mg/dL (any time blood is sampled for epinephrine) until hypoglycemia BG < 60 mg/dL and recovery BG ≥ 80 mg/dL has been achieved.
 - **Recovery Period:**
 - Blood will be sampled for epinephrine every 15 minutes for a total of 4 samples after the nadir blood glucose.
 - The actual time (rounded to the nearest minute) of all blood draws and questionnaires per the study clock set to an atomic clock will be documented on the nursing flow sheet.

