- 843 approved Gaymar T/pump heating pad.
- 844 ○ Intravenous access appropriate for blood drawing and potential
- 845 intravenous DW10 rescue will be established.
- 846 ○ The subject’s current pump parameters will be reviewed by the study
- 847 physician and documented. Any insulin boluses administered on the
- 848 day of admission will be recorded.
- 849 ○ Aside from administered meals and carbohydrate rescue, the subject
- 850 will remain fasting on the unit except for ad lib water and glucose-
- 851 free beverages. Caffeine will be restricted until blood sampling for
- 852 epinephrine is completed.
- 853 ○ Strenuous activity is restricted until blood sampling for epinephrine is

- 854 completed.
- 855 ○ Subjects and parents (or diabetes care partners) will be blinded to the
- 856 results of the glucose testing until the Recovery Period in an attempt
- 857 to eliminate bias when answering questions regarding symptoms of
- 858 hypoglycemia.
- 859
- 860 • **Procedures Related to the Run-in Period:**
- 861 ○ The Run-in Period will nominally occur from 07:30-08:00.
- 862 ○ The goal of the Run-in Period is to reach a target glucose of 100-150
- 863 mg/dL.
- 864 ○ Once IV access has been established, blood will be sampled for YSI
- 865 glucose every 5-30 minutes per the Blood Sampling guidelines above.
- 866 ○ Blood will be sampled for epinephrine at the initial sampling time for
- 867 YSI glucose.
- 868 ○ Fast acting carbohydrates may be used to stabilize the glucose or treat
- 869 BG <100 mg/dL at any time during the Run-in Period.
- 870 ○ For glucose >150 mg/dL, correction boluses may be administered
- 871 with the home pump up to every 90 minutes for a maximum of 2
- 872 correction boluses. The amount of insulin administered will be
- 873 calculated using the subject's insulin sensitivity factor and a target
- 874 glucose of 120 mg/dL.
- 875 ○ Once BG is between 100 to 150 mg/dL, baseline Hypoglycemia
- 876 Symptom Questionnaires will be completed and blood will be
- 877 sampled for epinephrine and glucagon at the next scheduled sampling
- 878 time for YSI glucose.
- 879 ○ The Run-in Period may be extended until 11:00 to ensure that it has
- 880 been at least 90 minutes since the last correction bolus, at least 60
- 881 minutes since the last glucose <70 mg/dL, and at least 30 minutes
- 882 since the last carbohydrate treatment. The subject may enter the
- 883 Hypoglycemia Induction Period once these criteria are met and

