- 1970 1. Peak epinephrine
- 1971 2. Epinephrine AUC
- 1972 3. Epinephrine increase over baseline
- 1973 4. Hypoglycemia symptom ratings
- 1974 5. Clarke Hypoglycemia Perception Awareness score
- 1975 6. Fear of hypoglycemia scores

1976

1977 Additional secondary endpoints of reduction in hypoglycemia will be assessed by:

- 1978 1. CGM time <70 mg/dL and <50 mg/dL by retrofitted CGM and SMBG trace from 1
 1979 week of blinded use versus the last week of intervention
 - 1980 a. During 24 hours, and
 - 1981 b. Overnight (11PM – 7AM)

1982

1983 Additional secondary endpoints of improvement in glycemic control at baseline versus the
 1984 last week of intervention will be assessed by:

- 1985 1. Time within target (70-180 mg/dL) over a 24 hour period
- 1986 2. Time within target range of 80-140 mg/dL overnight (11PM – 7AM), and
- 1987 3. Distribution of wake-up glucose levels at 7AM

1988

1989 **K. SUCCESS CRITERIA / GOAL**

1990 As a general rule, a subject’s data will be considered useful for data analysis if the
 1991 subject completes at least 1 week of study intervention with USS Virginia+AP system or
 1992 SAP.

1993 **L. STATISTICAL ANALYSIS PLAN**

1994 Sample size determination is based on literature data (#3) and on results from our
 1995 previous studies of hypoglycemia unawareness (#4)(#5). We estimate, conservatively,
 1996 that the effect size of using the AP system+USS Virginia vs. CGM in terms of
 1997 restoration of epinephrine response will be moderate ~0.35. Power calculations assuming
 1998 $\alpha=0.05$, and power of 80% yield a required sample size of N=36 (using G*Power 3
 1999 software [#5]). With this sample size, the power for finding significant effects on
 2000 frequency and extent of hypoglycemia (Low BG Index [#6]) exceeds 0.9. Assuming a
 2001 proportion of noncompliance R=20% for Intention-to-Treat (ITT) analysis (#7), 44
 2002 completed subjects will adequately address the specific aims of this study. Per-protocol
 2003 analysis will also be performed. In order to achieve 44 completed subjects, up to 70

2004 subjects may sign consent given an expected screen failure, withdrawal and drop-out rate
2005 of ~40% due to the rigorous exclusion criteria and requirements imposed for the AP
2006 system use in the subject's local environment.
2007
2008

2009 REFERENCES

- 2010 #1 Diabetes Research in Children Network (DirecNet) Study Group, Tsalikian E,
2011 Tamborlane W, Xing D, Becker DM, Mauras N, Fiallo-Scharer R, Buckingham B,

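### The pre-induction epinephrine and symptom baseline is triggered by glucose alone, can precede the protocol's own induction-entry criteria, and is not identified as the baseline for the increase-over-baseline endpoint

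*Combined protocol and SAP*

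**What the plan says.** All references are to the combined protocol and SAP.

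- **Trigger for the baseline set.** Section G.3 states it twice. Under the blood sampling instructions: "Once BG is between 100 to 150 mg/dL, baseline". Under the Run-in procedures: "Once BG is between 100 to 150 mg/dL, baseline Hypoglycemia". The questionnaires follow, and blood is "sampled for epinephrine and glucagon at the next scheduled sampling" time. In this glucose range the YSI schedule is "BG >100-200: every 15 minutes"; at 100 mg/dL or below it is every 5 minutes.
- **Criteria for entering induction.** A later bullet of the Run-in procedures allows extension to 11:00 so that it has "been at least 90 minutes since the last correction bolus, at least 60" "minutes since the last glucose <70 mg/dL, and at least 30 minutes" since carbohydrate. The subject enters induction when these are met and glucose is 100-150 mg/dL.
- **What may happen beforehand.** During the Run-in, carbohydrate may be given at any time, and up to two correction boluses may be given for glucose above 150 mg/dL. On the morning of admission (Section G.2, Preparation for Visit 3): "The subject may administer a correction bolus of insulin to stabilize BG or treat" hyperglycemia. Fast-acting glucose is also allowed then.
- **Another early sample.** Epinephrine is also drawn at the first YSI sample, with no condition on glucose or timing.
- **Endpoint.** Sections D and J list "Epinephrine increase over baseline" as a secondary endpoint. Neither names the sample meant.
- **Follow-up.** Section G.9 applies the same inpatient procedures at Visit 6.

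**The concern.** The protocol sets conditions for starting induction but does not apply them to the measurement from which the response to induction may be calculated. A subject who has just been low, or has just been given carbohydrate or insulin, must wait before induction starts. The baseline questionnaire and hormone sample need not wait, and are not repeated when the wait is over.

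At stake is one named secondary endpoint. If the 100-150 mg/dL sample serves as its baseline and is drawn soon after a low glucose, epinephrine may still be raised and the measured increase would be too small. The endpoint belongs to the counterregulation family, and Section L bases the sample size on the epinephrine response, without saying which epinephrine measure.

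The missing definition adds to this. There are two candidate pre-induction samples, and the initial one is even less controlled. In Sections D and J the word baseline also denotes the pre-intervention assessment, so the endpoint's wording does not settle the matter.

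**Working it through.** **1. The plan's draw budget.** Section G.3 expects about 31 glucose, 11 epinephrine and 2 glucagon draws.

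- Discard centers: 31×2 + 11×2 + 2×2 = 88 cc, as stated.
- Blood-sparing centers: 31×1 + 11×2 + 2×2 = 57 cc, as stated.

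The two glucagon draws are accounted for by one at baseline and one below 60 mg/dL. Itemised epinephrine draws come to 1 initial + 1 baseline + 4 in induction + 4 in recovery = 10, against about 11. A repeat of the full baseline set is therefore not budgeted.

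**2. Can the baseline come before the criteria?** I stepped through the protocol's YSI intervals (30 minutes above 200, 15 minutes above 100 to 200, 5 minutes at 100 or below). Let glucose start at G₀ at the time of the event and change by r mg/dL per minute. The trigger time T is the first scheduled sample with G₀ + r·T between 100 and 150. Blood follows one interval later, usually T + 15.

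Example: G₀ = 69, r = 2. At 15 minutes glucose is 99; at 20 minutes it is 109, so T = 20 and blood is drawn at 35 minutes.

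The rates are assumptions: +1 to +3 when rising, −0.5 to −2 when falling.

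| Event at time 0 | Questionnaire (min) | Blood (min) | Entry criterion (min) |
|---|---|---|---|
| Glucose 69, rising | 15-35 | 30-50 | 60 |
| Carbohydrate at 85-95 | 5-15 | 10-25 | 30 |
| Carbohydrate at 69 | 15-35 | 30-50 | 30 (met by the blood draw) |
| Bolus at 160-180, falling | 15-60 | 30-75 | 90 |
| Bolus at 220, falling | 45-150 | 60-165 | 90 |
| Bolus at 280, falling | 75-270 | 90-285 | 90 (met by the blood draw) |

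The gap is reachable for each of the three criteria. It closes after boluses at high starting glucose or with slow falls. The 30-minute figure in the first row needs 3 mg/dL/min, which in a straight line takes glucose to 69 + 3×30 = 159 by the draw, so it is an extreme. The questionnaire column assumes completion at the trigger. If the next-sample wording covers the questionnaire too, its times equal the blood times.

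**3. Can the baseline be remote from induction?** With glucose in range at 07:30, blood is drawn at 07:45. Suppose glucose then drifts above 150 and both permitted boluses are given, at 08:00 and 09:30. The 90-minute criterion is met at 09:30 + 90 min = 11:00, the latest permitted entry. The gap is 11:00 − 07:45 = 3 h 15 min; from a draw at 08:00 it is 3 h. Both boluses fall between baseline and induction.

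**4. Effect on the endpoint.** Measured increase = peak − baseline. A residual elevation δ at baseline gives (peak − baseline) − δ, a one-for-one loss. If a share p of an arm is affected, the arm mean falls by p·δ. The arm comparison is biased only if p·δ, or its change from Visit 3 to Visit 6, differs between arms; otherwise the effect is added noise. The documents give neither p nor δ, and no epinephrine level, SD or decay time, so no number can be put on it.

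**The case against.** The strongest reply is that early sampling is permitted, not usual. Preparation for Visit 3 asks for fingersticks at 03:00 and 06:00, a steady 100-150 mg/dL on arrival, and allows glucose below 100 to be treated beforehand. A subject with no recent low, carbohydrate or bolus already meets the entry criteria when the baseline is taken. This stands: the point is that the baseline can precede the criteria, not that it does.

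Second, a reader might infer that the protocol itself treats 60 minutes as the time epinephrine needs to clear. It does not. No reason is given for the waits, and the Run-in and its extension are described as serving glucose stabilization. Only the criterion for glucose below 70 bears directly on residual epinephrine. The documents do not show that carbohydrate or insulin alone alters it. Those two waits matter here only because the protocol sets them before induction and not before the baseline.

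Third, a reader might infer a bias in favor of the closed-loop arm through more arrival lows among controls. The documents do not support this. Both arms are tested at Visit 6 on home pump therapy, within about a week of finishing the intervention and by identical procedures; the opposite direction is as arguable.

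Fourth, the symptom endpoint is listed as ratings at baseline versus follow-up, naturally Visit 3 versus Visit 6. A change from the Run-in questionnaire is not a listed endpoint. The questionnaire's timing deserves the same repair, but no endpoint loss should be claimed for it.

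None of this removes the two facts that remain: the timing rule allows a premature or remote baseline, and the endpoint's baseline is not identified.

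**Conclusion.** The point holds as a cheap improvement to one secondary endpoint. As written, the baseline set may be taken before the protocol's own induction-entry criteria are met, or about 3 hours before induction, at both Visit 3 and Visit 6, with no repeat required. Under the assumed glucose rates, the epinephrine sample can fall 10 to 30 minutes short of the 60-minute criterion after a low (60 − 50 and 60 − 30).

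The reading that increase over baseline is generally contaminated, or reduced by a stated percentage, goes beyond the documents. The share of subjects affected, the size of any residual elevation and the between-arm direction are all unknown. The effect on the endpoint also assumes that the 100-150 mg/dL sample is its baseline, which the plan does not say.

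Peak epinephrine does not use a baseline. AUC is affected only if it is baseline-corrected, which is not stated. The primary endpoint, LBGI from CGM, is unaffected.

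**What to change.** In both places in Section G.3 where the trigger appears, tie the baseline questionnaire, epinephrine and glucagon to the last YSI draw before induction starts, once the existing entry criteria are met. If a set was taken earlier, repeat it then. In Sections J and L, define that last pre-induction epinephrine value as the baseline for increase over baseline, at both Visit 3 and Visit 6, and state whether AUC is baseline-corrected.

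Deferring the existing set adds no blood. A repeat adds 2 cc epinephrine + 2 cc glucagon = 4 cc, against 57 to 88 cc per admission. For adults, screening plus two admissions at a discard center with a repeat at each is at most about 25 + 2×(88 + 4) = 209 cc, against the 400 cc limit. For subjects under 18 the weight-based limits still have to be checked individually. Staff also need to take the set when the criteria are confirmed, which may cost up to one 15-minute sampling interval. No treatment or glucose-management rule changes.
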